2.5 Potential Risks and Benefits

2.5.1 Potential Risks

Influenza Illness

Common symptoms of common influenza illness includes: body aches or pains, chest congestion, chest tightness, chills, congested or stuffy nose, coughing, diarrhea, difficulty swallowing, eyes sensitive to light, fatigue, feeling dizzy, fever, head congestion, headache, lack of appetite, swollen lymph nodes, nausea, runny or dripping nose, scratchy or itchy throat, shivering, sinus pressure, sleeping more than usual, sneezing, sore or painful eyes, sore or painful throat, stomach ache, sweating, teary or watery eyes.

Moderate complications of influenza, which are unlikely to occur in healthy persons who participate in this study include: sinus infections and ear infections.

Severe complications of influenza, which are also unlikely to occur in healthy persons who participate in this study include: pneumonia, severe dehydration, severe bronchitis, myocarditis, myocardial infarction, pericarditis, Guillain Barré Syndrome/Bell's Palsy, transverse myelitis, encephalitis, worsening of chronic health conditions, admission to hospital, hypoxemia/respiratory failure, arrhythmia/cardiac arrest, and death.

These known risks of complications associated with an influenza infection are to be mitigated by active management by skilled research staff clinicians, including treatment with antiviral therapy (oseltamivir or baloxavir) when indicated. More details of these measures are described in Sections 6.4, 6.5, and 6.6.

Onward Transmission of Influenza Virus

Recipients, through participating in this study, might acquire influenza infection and transmit onwards to contacts outside of the trial, who might include vulnerable individuals. To mitigate this risk, recipients will be isolated and observed for approximately three days after last exposure, which is longer than the 24-48 hour incubation period for influenza, and treated with antiviral therapy prior to discharge if infection is detected.

Blood Draws

Drawing blood may cause transient discomfort and fainting. Lightheadedness or fainting is usually

self-limited and managed by having the subject lie down and elevate his/her legs, until the vasovagal response subsides. Bruising at the blood draw site may occur but can be prevented or lessened by applying pressure to the blood draw site for a few minutes after the blood is taken. Drawing blood may cause infection. The use of aseptic technique by designated clinical team members will make infection at the site where blood will be drawn unlikely.

Nose swabs or nose washes

Obtaining nose fluid or a nose swab may cause brief discomfort of the nares, a gag reflex, bleeding of the nose, watery eyes, or coughing during the collection.

Saliva Samples

We will ask participants to stop eating and drinking for about 30 minutes before giving a saliva sample, about $\frac{1}{2}$ teaspoon, in a specimen cup or tube. Giving a saliva sample may be difficult if participants' mouths are dry. To help with that, participants may drink a small amount of water 5 minutes before giving a sample.

Exhaled breath sampling

Exhaled breath sample collection is performed with a specialized apparatus which requires the participant to be seated in a humidified booth or tent with their face at opening (entrance) to the apparatus' large funnel. Participants will be able to breath normally and cough spontaneously. Participants will be asked to vocalize (e.g., say 'whoooooo', sing 'Happy Birthday', or yell a sports team cheer) periodically during sample collection. The existing apparatus is called the Gesundheit-II (G-II, U.S. Patent No. 8250903). As newer devices become available through the Advanced Bioaerosol Technology Core, we may supplement or replace the G-II with newer sampling equipment that may not require a humidified booth. A maximum of two 30-min samples will be collected each day with at least a 10-minute break between samples.

Breath samples may also be collected by breathing humidified air through a spirometer mouthpiece (EasyOne[®], NDD Medical Technologies, Inc) for 15 minutes while wearing a nose clip. Participants will be able to rest for 1 minute at 5-minute intervals during sample collecting via the mouthpiece. Participants will be asked to breath slowly and deeply (slow vital capacity maneuver) and may be asked to vocalize (e.g., say 'whoooooo') while breathing through the mouthpiece. A maximum of two 15-minute samples will be collected per day via breathing through a mouthpiece.

Breath samples may additionally be collected with a device that resembles a handheld peak flow meter. Participants will be asked to blow through the device several times, each time taking deep breaths. They may be asked to vocalize (e.g., say 'whoooooo') while breathing through the mouthpiece. These samples will take about 2 minutes to collect.

Total time breathing into a breath sampler will be limited to a total of 1 hour per day for the longer duration samples and 10 min for the 2-minute samples. Sampling will be performed daily for the duration of participant by Donors. Recipients will be asked to provide samples daily for up to four days after onset of symptoms or evidence of infection by laboratory testing.

The G-II presents no breathing resistance. Rarely for some persons, they may feel slightly claustrophobic sitting in front of the G-II cone. Breathing into the spirometer or peak flow meter-

like mouthpiece with a nose clip may cause dry mouth and discomfort from the nose clip. Some people may experience dizziness or lightheadedness due to the slow vital capacity breathing maneuver being employed. The breathing maneuver may also stimulate coughing. There is no noticeable resistance to breathing and the procedure has been well tolerated previously by people infected with influenza and other respiratory viruses. The short duration of the sample collection helps mitigate this discomfort, and the participant will be encouraged to breath slowly to reduce the risk of dizziness.

Loss of Confidentiality

Study participants will be asked to provide personal health information and other identifying information. To preserve protected health information (PHI) and confidentiality, identifying participant data will be kept in a locked, secured facility at the study site. All collected specimens will be coded, removing identifying information, prior to appropriate storage in a locked, secured, monitored facility, accessible only by designated personnel at the study site. The coded specimens will be able to be linked to identifying information which is only accessible to the clinical research staff. Specimens will be shared with EMIT-2 collaborating laboratories; collaborating lab personnel will not have access to identifying data.

Video and Digital Photos

Video footage or digital photos taken during the transmission experiments are to be analyzed and then either de-identified (by blurring or obscuring faces and other identifying marks) or erased by the end of the study. Video footage and digital photos will be recorded onto encrypted, password protected local devices (e.g., USB “thumb” drive) and only be made accessible to pre-designed study team members who will store video files in a password-protected electronic storage device or password-secured campus server drive.

Special Considerations for COVID-19

During the period when the U.S. Public Health Emergency exists for COVID-19, there is a risk of exposure to others with COVID-19 infection. We will minimize this risk by testing for COVID-19. Likewise, all study personnel will follow the most up-to-date CDC guidelines on personal protective equipment throughout the conduct of the Donor enrollment and conduct of the CHIVITT studies. Extensive controls to limit aerosol exposures using ventilation, filtration, and germicidal UV will also be employed throughout the test facility, outside of the exposure room, including individual rooms and hallways.

Risks with oseltamivir phosphate (TAMIFLU®) antiviral

Adverse events reported in at least 1% of adult and adolescent subjects treated with oseltamivir phosphate included nausea (10%), vomiting (9%), diarrhea (7%), bronchitis (2%), abdominal pain (2%), dizziness (2%), headache (2%), cough (1%), insomnia (1%), vertigo (1%), and fatigue (1%). [\[package insert\]](#)

Influenza A virus isolates with reduced susceptibility to oseltamivir carboxylate have been recovered by serial passage of virus in cell culture in the presence of increasing concentrations of oseltamivir carboxylate, from clinical isolates collected during treatment with oseltamivir, and from viral isolates sampled during community surveillance studies. Reduced susceptibility of influenza virus to inhibition by oseltamivir carboxylate may be conferred by amino acid

substitutions in the viral neuraminidase and/or hemagglutinin proteins. Changes in the viral neuraminidase that have been associated with reduced susceptibility to oseltamivir carboxylate. [\[package insert\]](#)

Risks of baloxavir marboxil (XOFLUZA®) antiviral

Adverse events reported in at least 1% of adult and adolescent subjects treated with baloxavir marboxil included diarrhea (3%), bronchitis (2%), nasopharyngitis (1%), headache (1%) and nausea (1%). [\[package insert\]](#)

Influenza A viruses with treatment-emergent amino acid substitutions at positions associated with reduced susceptibility to baloxavir marboxil in cell culture have been observed in clinical studies. It is theoretically possible that baloxavir marboxil treatment can cause treatment-emergent baloxavir marboxil resistant viruses. The overall incidence of treatment-emergent amino acid substitutions associated with reduced susceptibility to baloxavir marboxil in two prior clinical trials was 2.7% (5/182) and 11% (39/370). [\[package insert\]](#)

Rapid flu test

There are some risks associated with rapid flu tests. These tests can sometimes produce false-negative results, meaning that a person who actually has the flu is told that they do not have it. False-positive results are also possible, which can lead to unnecessary treatment and increased healthcare costs. Additionally, rapid flu tests have been known to have a lower sensitivity compared to other flu tests, meaning that they may not be as accurate in detecting the flu virus. Study participants will receive an information sheet that outlines the risks and benefits associated with rapid tests, as well as other instructions. The participants will be encouraged to discuss their test results with their healthcare provider for further guidance and treatment, if necessary.

Unknown Risks

There may be additional risks in this study which are not yet known.

There is also small risk to subjects who report that they are in good health but who have an unknown health problem at the time of screening. This study will screen by medical history through interview, a clinical questionnaire, clinical laboratories, and vital signs. Any clinically significant abnormalities discovered will be discussed with the participant and recommendations for appropriate referrals will be provided.

Potential Risks with Specimens and Data for Secondary Research

Specimens which may be left over after designated assays have been performed or extra specimens collected for secondary research may be indefinitely stored for future research. These specimens will be labeled with a code which will not contain personal identifying information. The risk of loss of confidentiality of a specimen is minimized by maintaining the linking information, to a subject and their personal information, in a secured and locked location with access only available to authorized study staff members.

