Should a recipient become laboratory-confirmed influenza infected (a countable SAR) and have accompanying symptoms during the CHIVITT, then the Recipient may be allowed to continue in the CHIVITT as a Donor. In order to accept the Recipient into the Donor status, the Donor informed consent form must be reviewed and signed by the participant. Recipients who are a countable SAR and do not want to continue in the CHIVITT may be safely discharged, contingent upon the absence of sufficient illness which may require treatment of influenza ([section 6.6](#)). However, once the 2 weeks have transpired, and if they have not become influenza infected, they will be allowed to end their participation in the CHIVITT. Recipients will also be allowed to withdraw from the study early, for their own personal reasons (see [section 6.7](#)).

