6.6 Treatment of Influenza

For the healthy young adult, influenza infection is largely a self-limiting viral infection which only requires rest and supportive care. No later than 72 hours of a Recipient demonstrating any criteria which satisfy the primary outcome of SAR influenza infection and immediately upon onset of fever $>102^{\circ}\text{F}$, meeting other criteria for a grade 3 adverse event (see Appendix A), or as required by the clinical judgement of study physicians, therapeutic intervention with an approved influenza antiviral agent (i.e., oseltamivir or baloxavir marboxil) will commence. Meanwhile, the subject will be requested to provide exhaled breath specimens; the subject will not be required to participate in additional *exposure event* group activities.

Recipients that become secondarily influenza infected may provide voluntary consent to continue in the CHIVITT as a Donor; the Donor consent form must be reviewed and signed in order for the participant to

continue as a Donor. Under this circumstance, treatment with the influenza antiviral agent will be withheld and the subject (now considered an infectious subject) will be instructed to participate in *exposure event* group activities, as a Donor participant. The participant may choose to terminate their participation as a Donor participant at any time before the maximum 5 days, as originally intended for a Donor participant. Upon deciding to terminate in participation in the CHIVITT, the subject can be administered an influenza antiviral agent and may be discharged. Under all circumstances, symptoms of an influenza infection are intended to be followed to resolution and this may be done through phone call contacts upon discharge; the dates of resolution of influenza symptoms are intended to be documented.

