6.9 Discharge Criteria

Subject discharge is planned at approximately 14 days (for Recipient participants) or 2-5 days (for Donor participants) after entry. To be eligible for discharge home, the participant must meet the following criteria: no greater than moderate severity influenza signs or symptoms (Appendix A) and are clinically stable during their stay. In addition, the participant must attest that they feel well enough to provide their own self-care. Otherwise, Recipients will be discharged as described in escalation of care (Section 6.8). Recipients must be at least 2 days post the end of their last exposure event to be eligible for discharge. We may discharge Recipients with a home influenza test to ensure that we do not miss late onset, long latency, influenza infection. However, recipients who have contracted the flu but do not wish to be a donor may be discharged earlier. In this case, they must meet the discharge criteria described above for discharge home. All other instances will be handled as described in Section 6.8.

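### The onward-transmission safeguards in section 2.5.1 (about three days of isolation, and an antiviral before an infected Recipient leaves) are not guaranteed by the discharge and treatment rules in 6.4, 6.6, 6.9 and Appendix D

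*Protocol*

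**What the plan says.** Section 2.5.1 of the protocol names the risk that Recipients infect contacts outside the trial, some of whom may be vulnerable. It offers two mitigations. The first covers every Recipient: "recipients will be isolated and observed for approximately three days after last exposure, which is longer than the 24-48 hour incubation period for influenza". The second covers infected Recipients, who are to be "treated with antiviral therapy prior to discharge if infection is detected".

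The operative rules are elsewhere:

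- Section 6.9, minimum stay: "Recipients must be at least 2 days post the end of their last exposure event to be eligible for discharge".
- Section 6.9, exception: "recipients who have contracted the flu but do not wish to be a donor may be discharged earlier". They must still meet the general criteria for going home, namely "no greater than moderate severity influenza signs or symptoms (Appendix A) and are clinically stable during their stay", and attest that they can care for themselves.
- Section 6.4: infected Recipients who do not wish to continue "may be safely discharged, contingent upon the absence of sufficient illness which may require treatment of influenza".
- Section 6.6: an antiviral is to start "No later than 72 hours of a Recipient demonstrating any criteria which satisfy the primary outcome of SAR influenza infection", and at once for high fever, other grade 3 criteria or on clinical judgement.
- Section 6.6, Recipient who has become a Donor: the antiviral is withheld while the person acts as Donor. On ending participation, "the subject can be administered an influenza antiviral agent and may be discharged".
- Appendix D, Recipient schedule: the antiviral falls within 72 hours of infection, and a footnote exempts those who continue as Donors.

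**The concern.** Section 2.5.1 tells the ethics board and the sponsor how people who have not consented to the trial are protected. That account should follow from the rules for discharge and treatment. Here staff could comply fully with 6.4, 6.6 and 6.9 and still release a Recipient sooner than 2.5.1 says, or release a known infected Recipient without the antiviral that 2.5.1 says comes first. The stated mitigation would then not describe what the protocol instructs. This is a contradiction within the protocol, and not a detail that a statistical analysis plan would settle.

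**Working it through.** The plan gives no statistical figure to reproduce on this point. The check sets the sections side by side, with a conversion of days to hours.

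**Isolation interval**

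Inputs: incubation period 24 to 48 hours and isolation of about 3 days (both 2.5.1); minimum of 2 days after the last exposure event (6.9).

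Margin = isolation time minus upper incubation limit.

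- Section 2.5.1: 3 × 24 = 72 hours; 72 − 48 = 24 hours.
- Section 6.9 floor: 2 × 24 = 48 hours; 48 − 48 = 0 hours.

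At the floor, isolation equals the upper limit, so the statement that it is longer fails there.

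The floor can occur in practice. Section 6.1 has a two-day run-in and lets exposure events spread over up to 9 or 10 days, and 6.9 plans discharge at about day 14. That leaves 14 − 2 − 10 = 2 days or 14 − 2 − 9 = 3 days after the last exposure.

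**Antiviral before discharge**

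Section 2.5.1 has one condition, that infection is detected. Three routes out do not carry it over:

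1. *Infected, declines to be a Donor, leaves early (6.9).* The criteria concern symptom severity, stability and self-care. None concerns antiviral treatment. The 72-hour limit in 6.6 and Appendix D runs from meeting an outcome criterion and is not linked to discharge, so a person who leaves before it expires need not have started treatment.
2. *Infected, declines to continue (6.4).* Release depends on not being ill enough to need treatment, with a cross-reference to 6.6. But 6.6 starts treatment on any criterion of the primary outcome, whatever the degree of illness. Under 6.6 every such person is due treatment; under 6.4 some are taken not to need it. The two do not fit together.
3. *Recipient turned Donor (6.6).* The antiviral is withheld during Donor participation, and the wording at exit is permissive.

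**Whether another section closes the gap**

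Section 8.1.7 requires an influenza test at discharge if none was done in the previous 12 hours, but attaches neither a hold nor treatment to a positive result. The home test in 6.9 is optional and is used after the person has left. The telephone follow-up of symptoms in 6.6 also comes after release. None of these supplies the two safeguards of 2.5.1.

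**The case against.** The strongest reply is that the sections can all be satisfied at once. The 2 days in 6.9 are a minimum, so a stay of about three days is allowed and fits the timetable. The 72 hours in 6.6 are a deadline, so treatment may start before discharge. Section 6.6 and Appendix D do require an antiviral for infected Recipients who do not become Donors. The permissive wording for Recipients turned Donors may only lift the earlier withholding. Daily testing after Donor exposure and the discharge test are real checks.

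Most of this stands, and it limits the point: the safeguards are possible but not guaranteed. It does not remove the conflict between 6.4 and 6.6, the missing antiviral condition for early leavers, or the failure of the incubation claim at the floor.

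A reader might infer more than the documents support:

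- *That the safeguards are never delivered.* A floor and a deadline do not show that.
- *That Recipients are released while still incubating.* On the protocol's own figures, 48 hours reaches the end of the stated period. Only the claim of a longer interval fails.
- *That the number affected follows from the 25% attack rate and 175 Recipients.* Section 2.3 gives 25% as the target under low air hygiene, and section 9.2 assumes reductions of 76% and 79% with intervention. The product would also count every infected Recipient, not those who leave early or untreated.
- *That the primary outcome loses late cases, or is biased by the order of air-hygiene conditions.* The documents give no share of infections first detectable after 48 hours. The outcome also counts serology, with blood taken at about one month, and no condition is fixed as last.

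**Conclusion.** The contradiction holds on both limbs. For isolation, the margin over the stated upper incubation limit is 24 hours under 2.5.1 and 0 hours at the 6.9 minimum. For the antiviral, 2.5.1 makes it a condition of discharge for infected Recipients, while 6.4, 6.6, 6.9 and Appendix D leave routes by which such a person may go without having started it. Section 6.4 also conflicts with 6.6 directly.

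The conclusion rests only on the protocol's wording and its own incubation figure. It says nothing about how often the gap would be used, and the documents do not allow a count. No effect on power or on the attack-rate analysis is claimed. It needs correcting because it concerns the stated protection of third parties.

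**What to change.** Reconcile 2.5.1, 6.4, 6.6, 6.9 and Appendix D so that they give:

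- one post-exposure isolation interval for Recipients, in the same terms throughout;
- one statement on whether an antiviral is given before an infected Recipient leaves, expressly covering early leavers who decline Donor status and Recipients turned Donors, with the condition in 6.4 brought into line with 6.6.

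If the 2-day floor is kept, delete from 2.5.1 the claim that isolation exceeds the incubation period. Which interval and which treatment rule are right is for the sponsor's clinicians, and no view is taken here.

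The cost is protocol wording. If the longer interval is chosen, it is also up to one extra hotel night for some Recipients (3 − 2 = 1 day).

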6.2 Duration of Donor Participation

It is intended that symptomatic influenza-infected Donors be introduced into the CHIVITT as soon as possible after onset of symptoms, while still shedding influenza viruses. When the daily influenza testing (e.g., using BioFire Respiratory Panel testing or exhaled breath testing) demonstrates no detectable virus, which is anticipated to occur by approximately 3 to 5 days from the initiation of symptoms, or more than three days has elapsed since onset of symptoms, discharge plans for the participant may be entertained. Safe discharge will be contingent upon the absence of sufficient illness which may require escalation of care ([section 6.8](#)). Donors may also be allowed to withdraw from the study early, for their own personal reasons ([section 6.7](#)).

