6.5 Staffing of the Facility

The facility will be staffed by research team members who will be present in the facility 8 am through 5 pm each day (including weekends). An on-call physician will be available for all hours, including evenings and weekends, for the management of illness or to address any questions or concerns from any study participants. The on-call physician can make decisions on the treatment of influenza, use of supportive care, and escalation of care. For overnight hours, a thermometer and over the counter antipyretics will be made available. Participants will be able to request video or phone call contact with the covering physician to discuss any concerns. The on-call physician will use their judgement whether they may need to report into the quarantine research unit to directly assess the participant.

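### Section 6.6 withholds antivirals from Recipients who become Donors without saying whether its immediate treatment triggers still apply, and the discharge rules do not carry through the treatment promised in 2.5.1.

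*Protocol*

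**What the plan says.** Section 2.5.1 gives two mitigations for onward transmission. One is that "recipients will be isolated and observed for approximately three days after last exposure", justified as exceeding an incubation period of 24 to 48 hours. The other is that Recipients will be "treated with antiviral therapy prior to discharge if infection is detected". The preceding paragraph, on illness risk, covers management that includes antivirals and adds: "More details of these measures are described in Sections 6.4, 6.5, and 6.6".

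The operative sections say the following.

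- **6.6, general rule.** The outer limit for starting an antiviral is "No later than 72 hours of a Recipient demonstrating any criteria which satisfy the primary outcome of SAR influenza infection". Treatment is immediate for fever above 102°F, other grade 3 criteria, or when clinical judgement requires it.
- **6.6, Recipients who become Donors.** The antiviral is withheld, and no exception is named. The person may stop at any time within the 5-day Donor maximum. On stopping, the drug is permitted and discharge may follow. Appendix D footnote 8 repeats the exemption.
- **6.2.** A Donor may leave once virus is undetectable, "or more than three days has elapsed since onset of symptoms, discharge plans for the participant may be entertained".
- **6.4.** "Recipients who are a countable SAR and do not want to continue in the CHIVITT may be safely discharged". The only condition attached is that the person is not ill enough to need influenza treatment, and the text cross-refers to 6.6.
- **6.5.** "The on-call physician can make decisions on the treatment of influenza, use of supportive care, and escalation of care".
- **6.8.** Antivirals are mandatory once escalation of care is recognised as necessary. Escalation is to be considered for a severe complication, shortness of breath with SpO2 below 89%, or two severe vital signs.
- **6.9.** Discharge requires no more than moderate influenza signs or symptoms, clinical stability and ability for self-care. Recipients must be at least 2 days past their last exposure, but infected Recipients who decline the Donor role may leave sooner. A home influenza test may be supplied.
- **8.1.3 and 8.1.7.** Influenza testing is daily, and is repeated at exit if the last test is more than 12 hours old.

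**The concern.** Section 6.6 contains two instructions that meet in the same patient and does not rank them. A Recipient-Donor with a grade 3 fever satisfies an immediate treatment trigger and also falls under the withholding rule. These are healthy volunteers exposed to influenza on purpose, so the precedence should be written down and not left to whoever is on call.

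The second matter concerns people outside the trial. Section 2.5.1 relies on antiviral treatment before discharge to protect contacts, some of whom it says may be vulnerable. The sections that govern leaving the unit do not contain that condition. Staff working from them could release a Recipient with detected infection before treatment starts.

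The isolation floor is a smaller instance of the same pattern: the operative minimum does not meet the rationale given in the risk section.

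**Working it through.** No planned figure needs reproducing. The check sets the texts side by side, with simple arithmetic on hours and counts.

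**1. Triggers against withholding.** Take a Recipient-Donor whose only abnormality is an oral temperature above 102.0°F.
- Appendix A: grade 3.
- 6.6, general rule: start antiviral immediately.
- 6.6, Recipient-Donor rule, and footnote 8: withhold.
- 6.8, vital-sign criterion: two severe signs needed, one present; 1 < 2, so not met.
- 6.5: the on-call physician decides.

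No sentence says which rule prevails. The ceiling on withholding is the Donor maximum, 5 × 24 = 120 h. Reaching it would require that neither physician nor participant acts.

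**2. Exit of a Recipient-Donor.** The promise in 2.5.1 has no exception for this group, while 6.6 is permissive at exit. Leaving does not imply viral clearance, because 6.2 accepts elapsed time as an alternative to undetectable virus and 6.6 allows stopping at will.

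**3. Early discharge of an infected Recipient who declines the Donor role.** Suppose discharge is on the day infection is detected (hour 0).
- 6.6 alone: treatment may start up to 72 − 0 = 72 h after discharge.
- 6.6 with 2.5.1: treatment starts by the earlier of discharge and 72 h, so the delay after discharge is 0 h.

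The second reading is available and consistent, but neither 6.4 nor 6.9 states it.

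**4. Isolation floor.**
- 6.9 minimum: 2 × 24 = 48 h. Margin over the 48 h incubation limit: 48 − 48 = 0 h.
- 2.5.1 plan: 3 × 24 = 72 h. Margin: 72 − 48 = 24 h.
- Exit test at the floor, by the letter of 8.1.7: up to 12 h old, so taken from 48 − 12 = 36 h after last exposure.
- If test and discharge both fall within the 8 am to 5 pm staffing in 6.5, a same-day test is at most 9 h old: 48 − 9 = 39 h. A test from 5 pm the day before would be 15 h old at 8 am and would have to be repeated.
- Exit test after a three-day stay: 72 − 12 = 60 h or later.

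**5. Scale.** Assume one attack rate for all Recipients.
- At the 25% expected in 9.2: 20 × 0.25 = 5 per cohort of 20, and 175 × 0.25 = 43.75, about 44 overall.
- At the 79% reduction assumed in 9.2: 0.25 × 0.21 = 0.0525, giving 20 × 0.0525 = 1.05 and 175 × 0.0525 = 9.19.

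These are expected numbers infected, not maxima. With 20 independent Recipients at 25%, more than 5 infections occur about 38% of the time. The protocol does not say what share would become Donors.

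**The case against.** The strongest reply is that nothing here forces a breach. Section 2.5.1 is protocol text and binds staff as much as 6.9 does. The 72 hours in 6.6 is an outer limit, and 6.4 cross-refers to 6.6. The discharge checklist in 8.1.7 includes a review of discharge medications. A Manual of Procedures, mentioned in section 11, may spell out the order of events. This stands to the extent that the early-discharge point is an omission, not a conflict. It does not remove the omission, because the conditions listed in 6.4 and 6.9 concern illness severity and fitness to leave, not whether treatment has begun.

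On withholding, physicians keep treatment discretion under 6.5, 6.8 preserves clinical judgement, and the participant can stop and be treated at any time. A reader might infer that the protocol forbids treating a febrile Recipient-Donor. The documents do not support that: treatment is possible. What is missing is the rule of precedence, and the withholding sentence taken literally points the wrong way.

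On isolation, a three-day stay satisfies both sections, testing is daily and repeated at exit, and the optional home test in 6.9 is aimed at late-onset infection. Those safeguards narrow the gap considerably. Nor is it a flaw that detected cases are exempt from the floor, since a wait based on incubation serves to find undetected infection.

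**Conclusion.** The point holds and should be fixed, in this order of weight.

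1. **Main point.** 6.6 and footnote 8 leave unresolved whether the immediate triggers end withholding for Recipient-Donors, and 6.6 makes the antiviral optional when they leave. The vital-sign criterion in 6.8 does not cover an isolated fever above 102°F.
2. **Second point.** The pre-discharge treatment promised in 2.5.1 is not carried into the early-discharge provisions of 6.4 and 6.9. A reader might infer a direct contradiction with a permitted delay of 72 h. That delay arises only if 6.6 is read without 2.5.1; read together it is 0 h.
3. **Lesser point.** The 6.9 floor leaves a 0 h margin over the stated incubation limit, against 24 h under the plan in 2.5.1.

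At a 25% attack rate the expected number infected is 5 of 20, or about 44 of 175. A reader might take these as upper bounds or as numbers harmed; they are neither. They rest on the assumed attack rate and describe the group to whom the treatment and discharge points could apply. The conclusion rests on the protocol wording alone. No effect on sample size, power or the primary analysis is claimed.

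**What to change.** - **6.6 and Appendix D footnote 8:** state that fever above 102°F, other grade 3 criteria or physician judgement end withholding at once.
- **6.6, exit of a Recipient-Donor:** replace the permissive wording with a requirement that the antiviral is offered and started, or refusal documented, before discharge.
- **6.4 and 6.9:** add the same condition for every Recipient with detected infection.
- **6.9:** raise the floor after last exposure to about 3 days, and in any case above 48 h, to match 2.5.1.

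The cost is an amendment, which needs IRB approval under 10.1. Some Recipient-Donors would be treated sooner and serve a shorter time as Donors. The longer floor may add up to about one hotel day per Recipient.
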